Medical University of South Carolina Protocol

PI Name: [name]

Study Title: Effects of Neuromodulation and Rehabilitation of the Locomotor Network in Freezing of Gait

TABLE OF CONTENTS –

- A. Specific Aims, page 1
- B. Background and Significance, page 1-2
- C. Preliminary Studies, page 2
- D. Research design and methods, page 2
- E. Protection of Human Subjects, page 3
- F. References, page 8
- G. Consultants, page 8
- H. Facilities Available, page 8
- I. Investigator Brochure, page 10
- J. Appendix, page 10

A. SPECIFIC AIMS

Aim 1: To determine the effects of supplementary motor area low frequency repetitive transcranial magnetic stimulation (SMA LF-rTMS) + rehabilitation compared to rehabilitation alone on the locomotor network in patients with PD and FoG.

Hypothesis: SMA LF-rTMS followed by rehabilitation will decrease connectivity between mesencephalic locomotor region (MLR) and SMA more so than rehabilitation alone.

Aim 2: To determine the effects of SMA LF-rTMS + rehabilitation compared to rehabilitation alone on FoG severity in patients with PD and FoG.

Hypothesis: SMA LF-rTMS followed by rehabilitation will improve FoG severity (as measured by objective and subjective markers of FoG severity) more so than rehabilitation alone.

B. BACKGROUND AND SIGNIFICANCE

FoG is a debilitating condition, which occurs in the majority of patients with PD¹⁻³. FoG often leads to falls, hospitalizations, or nursing home placement and has been found to be the most important predictor of poor health-related quality of life^{2,4-6}. Current treatment strategies aim to optimize response to available medical or surgical therapies; however, responses are limited, inconsistent and short lived. Previous rehabilitation strategies have yielded only modest improvements in gait parameters not FoG specifically, and there is no evidence of sustained efficacy. As our knowledge of the pathophysiology grows, we begin to understand that FoG is not purely a dopaminergic circuit phenomenon. Preliminary evidence from our group and others support the notion that FoG is a network dysfunction with significant contribution from cortical structures. Our observation of the reversibility of FoG following immobilization supports the plausibility of network modulation and rehabilitation as a therapeutic approach.

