rTMS Protocol: Active rTMS will be delivered to the bilateral SMA region at the following parameters: 1 Hz, 1200 total pulses, 110% resting motor threshold (rMT), 20 minutes total for ten total sessions. Sham stimulation will be administered using the Magventure B-65 placebo system in which the sham side of the coil was placed over the pre-SMA (no magnetism delivered) and electricity is delivered to scalp stimulating electrodes in the same pulse sequence as active stimulation replicating stimulation sensation. This device is FDA approved for Depression. Participants will be given a questionnaire to complete about their thoughts on the treatment. This will occur on the last day of the intervention period (10th day of intervention).

Rehabilitation Protocol: Subjects will undergo ten, 20 minute, dual task training sessions immediately following each rTMS session. Dual task training will consist of repetitive trials of straightaway walking and turning while adding increasingly difficult concurrent cognitive tasks (working memory language and calculation). Subjects will be instructed to focus on the cognitive task, not on their gait with the goal of improving gait without increasing error rate on the cognitive task. Variations of this protocol have been successfully implemented in this patient population^{8,9}.

Trial Design and outcomes: Subjects will be randomized to either active rTMS + rehabilitation or rehabilitation alone at a 2:1 ratio (10 active: 5 control). An additional 6 patients will be randomized to either active rTMS + rehabilitation or rehabilitation alone at a 1:2 ratio (2 active: 4 control). This will bring total number of subjects to 12 active and 9 control. The primary outcome measure will be dual task interference for turning.

Gait Assessment/Analysis Protocol: Gait is assessed at baseline and post intervention. Subjects will walk on an electronic walkway (GaitRite + M²) which will capture straightaway walking and turning, in the off medication and on medication state, under single and dual task conditions (2 trials each), capturing multiple spatiotemporal parameters. Dual task interference for overall task time (timed up and go), step length, velocity and nFOG-Q scores will be secondary outcomes. Gait assessment will be videotaped.

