Statistical analyses: The sample size estimation is based on the primary (mechanistic) aim (Aim 1), since the effect size of the clinical aim (Aim 2) has not yet been established. A two group t-test with a 0.05 two-sided significance level will have 80% power to detect the difference between a treatment group mean of 0.11 and a control group mean of -0.06 assuming that the standard deviation is 0.10, when the sample sizes in the two groups are 12 and 9, respectively (a total sample size of 21). The mean and standard deviation estimates are based upon the functional connectivity strength for the FOG+ and combined control groups as reported in Fling et al 2014¹⁰. The observed treatment effects on FoG severity of the treatment group, as compared to the control group, will be used to determine the effect size of this therapy, and estimate the sample size for future trials aiming to determine efficacy.

E. PROTECTION OF HUMAN SUBJECTS

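### The stated 80% power is wrong for 12 and 9 subjects: the plan's own inputs give 95.5%, 80% fits the first-stage 10:5 allocation, and the group means run against the Aim 1 hypothesis

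*Combined protocol and SAP*

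**What the plan says.** The Statistical analyses paragraph in section D sizes the trial on Aim 1, because no effect size has been established for Aim 2. The test is specified as "A two group t-test with a 0.05 two-sided significance level". The paragraph says this test "will have 80% power to detect the difference between a treatment group mean of 0.11 and a control group mean of -0.06", with a standard deviation of 0.10, "when the sample sizes in the two groups are 12 and 9, respectively (a total sample size of 21").

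On the source of these values it says: "The mean and standard deviation estimates are based upon the functional connectivity strength for the FOG+ and combined control groups", as reported in a cited imaging study.

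The paragraph on trial design and outcomes in the same section builds the 21 subjects in two steps. The first is: "Subjects will be randomized to either active rTMS + rehabilitation or rehabilitation alone at a 2:1 ratio (10 active: 5 control"). A further six patients are then randomised 1:2 (2 active, 4 control), giving 12 and 9.

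The Aim 1 hypothesis in section A is: "SMA LF-rTMS followed by rehabilitation will decrease connectivity between mesencephalic locomotor region (MLR) and SMA more so than rehabilitation alone". Section C reports higher connectivity between the pedunculopontine nucleus and the motor network, including the SMA, in patients with freezing than in Parkinson's controls. No allowance for dropout is stated.

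**The concern.** The sentence gives every input to a standard calculation, so the power can be checked directly. A difference of 1.7 standard deviations with 21 subjects should give well over 80%.

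Two features of the inputs also look wrong. The values are described as connectivity strengths, and the treatment group has the higher one, although the treatment is expected to lower connectivity. And the difference comes from comparing freezers with controls, whereas every subject in this trial has freezing of gait.

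At stake is the only quantitative basis for 21 subjects. A reader of a null Aim 1 result would take it that the trial had 80% power for a difference of 0.17. That is not so, and the paragraph does not say what the trial could have detected with 80% power. Nor does any stated calculation explain the six added patients, since on the same inputs 10 and 5 already exceeded 80%.

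**Working it through.** **Inputs** (all from the Statistical analyses paragraph, except the 10:5 allocation, which is from the trial design paragraph)

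- Means 0.11 and −0.06: difference 0.11 − (−0.06) = 0.17
- SD 0.10: standardised difference d = 0.17 / 0.10 = 1.7
- Two-sided alpha 0.05, two-group t-test
- n₁ = 12, n₂ = 9; first stage 10 and 5

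**Formula.** Power of the pooled t-test is the probability that a noncentral t variable with df = n₁ + n₂ − 2 and noncentrality d × √[n₁n₂/(n₁ + n₂)] exceeds the two-sided 5% critical value in absolute size.

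**Attempt to reproduce the plan's 80%**

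| Allocation | df | Noncentrality | Critical t | Power |
|---|---|---|---|---|
| 12:9 (as stated) | 19 | 1.7 × √(108/21) = 3.855 | 2.093 | 95.5% |
| 10:5 (first stage) | 13 | 1.7 × √(50/15) = 3.104 | 2.160 | 81.8% |

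The 80% does not reproduce at 12:9. Other versions of the calculation at alpha 0.05 do not recover it either:

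- normal approximation, two-sided: 97.1%
- one-sided t-test: 98.1%
- Welch t-test (simulated): about 95.1%
- Mann-Whitney test (simulated): about 93.1%

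An unstated dropout allowance would have to be large. Assumed losses of 10%, 20% and 30% (11:8, 10:7, 8:6) give 93.1%, 89.6% and 82.3%.

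**What 80% means at 12:9.** Solving the same formula for 80% power gives d = 1.302, a difference of 0.130 at SD 0.10, which is 0.130/0.17 = 77% of the assumed gap. Alternatively, the difference stays at 0.17 and the SD is about 0.131. Neither 0.130 nor 0.131 appears in the plan.

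**Likely origin.** With identical inputs, 10:5 gives 81.8%, and 10:5 is the first stage of the protocol's own build-up to 12:9. That makes a carried-over figure plausible. It is not proof: 9:5 gives 79.9% and 7:6 gives 79.4%.

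**Direction.** Section C puts freezers above controls in connectivity. Taken in sentence order, 0.11 is the freezing-group value and −0.06 the control-group value, yet they are assigned to the treatment and control arms of this trial. As connectivity levels, they place the treated arm 0.17 above the rehabilitation-only arm. Aim 1 predicts that it will be below.

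**Size of the assumed effect.** On the same reading, a between-arm difference of the full 0.17 amounts to active treatment bringing freezers all the way to control-group connectivity while rehabilitation alone leaves it unchanged. Power at 12:9 with SD 0.10 if the between-arm difference is smaller:

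| Share of the 0.17 gap | Difference | d | Power |
|---|---|---|---|
| 100% | 0.170 | 1.700 | 95.5% |
| 75% | 0.1275 | 1.275 | 78% |
| 50% | 0.085 | 0.850 | 45% |
| 25% | 0.0425 | 0.425 | 15% |

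The fractions are illustrative; the plan gives no expected degree of normalisation.

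**The case against.** The strongest reply is that the error is conservative. On the plan's inputs the trial has more power than it claims, and it would keep about 82% even if 30% of subjects were lost. The sign of the difference does not alter the power of a two-sided test. A reader who has all the inputs can work out the detectable difference. All of this is true. It limits the harm but does not make the stated figure right, and readers should not have to redo the calculation to learn what the trial can detect.

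A second reply is that the direction point depends on how the values are read. The paragraph says only that they are based on connectivity in two groups. It does not say which value belongs to which group, or whether levels or changes are meant. Because imaging is done before and after the intervention, the means could have been intended as reductions, and the sign would then fit. That reading is possible, but the text calls the values connectivity strengths and says nothing of change. What stands is that the scale is undefined and that, read literally, it conflicts with Aim 1.

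Third, the calculation fixes only a between-arm difference, so full normalisation with no change in controls is one way to arrive at 0.17, not the only one. That is fair. It is nevertheless the reading that follows from using a freezer-versus-control contrast, and the plan offers no other. Naming the source and calling the work a pilot does not turn that contrast into an estimate of a treatment effect.

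The 10:5 origin remains an inference.

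**Conclusion.** The concern holds. For the test, alpha, means, SD and group sizes in the plan, power is 95.5%, an understatement of about 15 percentage points. At 12 and 9, 80% power belongs to a difference of 0.130, not 0.17. These results assume the pooled t-test with equal SDs of 0.10 and no dropout, as the sentence itself does, and the alternative methods tried at alpha 0.05 do not change the conclusion.

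The means, read as the connectivity strengths they are said to be, contradict the direction of Aim 1. The difference is borrowed from a contrast between people with and without the condition. The trial is not underpowered on its own inputs, but the apparent surplus should not reassure, because those inputs are optimistic: at half the assumed difference, power falls to 45%. The paragraph must be corrected, as it is the only sample-size justification in the protocol.

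**What to change.** Rewrite the power sentences in the Statistical analyses paragraph:

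1. State either about 95% power for a difference of 0.17, or 80% power for a difference of 0.13, in both cases with SD 0.10 and 12 and 9 subjects.
2. Define the scale. Either give the active arm the lower expected post-treatment connectivity, or express the effect as a between-arm difference in change from baseline, with an SD that belongs to that measure.
3. Say that 0.17 is a freezer-versus-control difference and that using all of it as the treatment effect assumes full normalisation relative to rehabilitation alone.
4. As a useful but optional addition, report power at 75% and 50% of that difference (78% and 45% at SD 0.10).

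The cost is the rewording of one paragraph. Patient numbers and study procedures do not change. If the sponsor moves to a change score, it will need an SD for change, which the protocol does not give, and the power must be recalculated from it.

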4. IMPORTANCE OF THE KNOWLEDGE TO BE GAINED

Identifying an effective means of measuring FoG severity will make it possible to test the efficacy of multiple potentially effective therapeutic agents. Understanding the pathways most related to FoG via our imaging protocols would yield potential therapeutic targets for this condition. Finally, collecting pilot data on this specific intervention may yield sufficient data to justify a larger trial.

5. SUBJECT SAFETY AND MINIMIZING RISKS (Data and Safety Monitoring Plan)

The participant is at minimal risk during the intervention; however, safety precautions will be taken by securing medical clearance for all participants. During the Motion Analysis and gait training portion of the study, subjects will be attended by the research therapist at all times. We do not anticipate any cardiovascular discomfort since subjects will not be asked to exert themselves in any way. Lab technician will take all necessary precautions including the use of a harness to avoid falls. Additionally, the participant will be aware that they may discontinue the study at any time. Subjects will be aware of all possible side effects at the time of screening and will be instructed to notify the PI or Co-PI immediately if they experience a side effect.

Internationally recommended TMS screening procedures will be completed prior to in person screening, during in person screening/enrollment, and prior to each rTMS session to minimize the chance that participants are at risk for severe risks associated with rTMS (e.g., seizures). Short term side effects such as migraine headaches can be minimized by recommending that participants take an OTC pain killer (e.g., Ibuprofen) on their own volition.

If an emergency should present, the facility is located on the MUSC campus with 24-hour access to the MUSC Emergency Room that is staffed by an emergency response team.

If during assessment of a subject's UPDRS score, the subject is found to be severely depressed or suicidal, the investigator will verify the patient's current mental health status and ensure the patient is directed and transported to the nearest psychiatric emergency services immediately or arrange for expedited evaluation by psychiatric services if the patient is not actively suicidal.

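### The observed effect in 12 v 9 patients is to set the effect size for later efficacy trials, with no stated allowance for its imprecision

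*Combined protocol and SAP*

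**What the plan says.** In the combined protocol and SAP, section D, the statistical analyses paragraph bases the sample size on the mechanistic Aim 1, "since the effect size of the clinical aim (Aim 2) has not yet been established". Its last sentence gives the only analysis stated for Aim 2. What is seen on freezing severity between the arms "will be used to determine the effect size of this therapy, and estimate the sample size for future trials aiming to determine efficacy".

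The trial design paragraph of section D fixes the numbers: "This will bring total number of subjects to 12 active and 9 control". It names dual task interference for turning as the primary outcome and lists several secondary gait and questionnaire measures. Gait is recorded on and off medication. The Aim 2 hypothesis in section A covers both objective and subjective markers. The sizing sentence does not say which of these measures supplies the effect size.

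Section E.4 describes the wider purpose: "collecting pilot data on this specific intervention may yield sufficient data to justify a larger trial". For this step the documents mention no confidence interval, shrinkage, conservative bound or minimum important difference.

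**The concern.** Using a pilot to inform a later trial is legitimate. The difficulty is letting the observed difference between 12 and 9 patients fix the effect size. A difference estimated from 21 people is compatible with anything from modest harm to a very large benefit, and a sample-size formula divides by its square. A pilot that overestimates the effect gives a later trial that is much too small. One that underestimates it gives an impracticably large trial, or leads to the therapy being dropped. Favourable pilots are more likely to be followed up, so the trials actually run would tend to be too small. Leaving the choice among several severity measures open could add to this.

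At stake is the stated product of the clinical aim, namely the effect size and sample size handed to whoever designs the efficacy trial.

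**Working it through.** **The plan's own figure.** There is none for Aim 2. The only calculation concerns Aim 1 connectivity: "A two group t-test with a 0.05 two-sided significance level will have 80% power" for "the difference between a treatment group mean of 0.11 and a control group mean of -0.06" with SD 0.10, so d = 0.17/0.10 = 1.7. At 12 v 9 an exact two-sided t-test gives 95.5%, not 80%; at 10 v 5 the same inputs give 81.8%. That mismatch is a separate matter and does not enter what follows.

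**Inputs.** Arms of 12 and 9 (section D), so 19 degrees of freedom. The true clinical d is not given and is an assumption; I use 0.2 to 1.7. The later trial is assumed to be 1:1, two-sided 0.05, with 80% power.

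**Step 1: precision of the pilot.**
- SE of d ≈ √(1/12 + 1/9) = √0.1944 = 0.441.
- 95% half-width = 2.093 × 0.441 = 0.92 SD.
- Observed d = 0.5: noncentral-t 95% CI -0.38 to 1.37.

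**Step 2: what this does to a sample size.** Per arm, n ≈ 2(1.96 + 0.84)²/d² + 1 = 15.68/d² + 1.
- True d = 0.5 needs 15.68/0.25 + 1 = 63.7, so 64 per arm.
- At true d = 0.5 the quartiles of the pilot estimate are about 0.20 and 0.82, and 13% of estimates are zero or negative.
- An upper-quartile pilot gives 15.68/0.82² + 1 = 24.3, so 25 per arm, with true power of about 41%.
- A lower-quartile pilot gives 15.68/0.20² + 1 = 393 per arm.
- Among positive pilots, the 10th to 90th percentile of the derived size is 13 to about 650 per arm.

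**Step 3: true power of the later trial.** At least 100,000 pilots were simulated for each true d. Each pilot with a positive estimate sized a trial by the formula above, and its power was then computed at the true d.

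| True d (assumed) | Later trials below 50% power | Below 80% |
|---|---|---|
| 0.2 | 63% | 74% |
| 0.3 | 52% | 67% |
| 0.5 | 37% | 58% |
| 0.8 | 26% | 52% |
| 1.0 | 17% | 50% |
| 1.2 | 15% | 47% |

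At d = 1.7, the size assumed for Aim 1 connectivity, about 4% fall below 50%. Replacing d by Hedges' g changes little (34% below 50% at d = 0.5). Counting all pilots at d = 0.5, including those with no positive estimate, 32% lead to a trial below 50% power.

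**Step 4: the alternative.** Size the later trial on a fixed target difference and take only the SD from the pilot. With target and true d both 0.5:

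| Basis for sizing | Below 50% power | Below 80% |
|---|---|---|
| Observed d | 37% | 58% |
| Fixed target, observed SD | 3% | 53% |
| Fixed target, upper one-sided 80% limit of the SD | under 1% | 19% |

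That upper limit is the observed SD × √(19/χ²), with χ² the 20th percentile on 19 degrees of freedom, a factor of 1.18.

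**The case against.** The strongest reply is that this concerns a trial not yet designed. Nothing in the present allocation, data collection or Aim 1 test changes, and any efficacy trial would need its own justified sample size. The plan openly says that the clinical effect is unknown and leaves efficacy to later work. That stands, and it is why the point is lower priority.

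A second reply is that the sentence is loose pilot wording. It does not exclude using an interval or a conservative bound, so a reader who infers a fixed rule of putting the raw estimate into a formula goes further than the text. That is fair as to mechanics. But the sentence does say that the observed effects will determine the effect size, and no other passage tempers it.

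Third, the size of the problem depends on an assumed d. This also stands. A reader might infer that the next trial would usually be badly underpowered, but the documents give no clinical effect on which to base that. At d of 1.0 or more, power below 50% is uncommon. They also give no evidence that the clinical effect is that large.

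Fourth, the share below 80% says little against the plan, because a correct target with the pilot SD still leaves 53% below 80% at d = 0.5. This is right; the share below 50% is the figure that separates the two approaches.

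**Conclusion.** The concern holds in a limited form. The plan lets an estimate with a 95% half-width of about 0.92 SD set the effect size for later trials, and states no allowance for that error. If the observed value is used directly and the pilot is positive, the chance that the next trial has true power below 50% runs from about 63% at a true d of 0.2, through 37% at 0.5, to 4% at 1.7. These figures assume normal outcomes, full retention, a 1:1 later trial and follow-up of any positive pilot. Dropout, for which the plan makes no allowance, would widen the interval.

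A reader might also infer that the pilot applies a go/no-go rule. The documents state none; section E.4 says only that the data may be enough to justify a larger trial. Nor does the point bear on patient safety, the conduct of this trial or its Aim 1 test. It limits what Aim 2 can legitimately conclude.

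**What to change.** Replace the last sentence of the statistical analyses paragraph with:

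> *Aim 2 will estimate the between-arm difference in dual task interference for turning (the primary outcome) with its 95% CI. The pilot will supply the SD, the baseline-post correlation and retention for planning; a later efficacy trial will be sized on a pre-stated minimum important difference, not on the observed mean difference.*

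Adding that the upper one-sided 80% confidence limit of the SD will be used would also deal with most of the shortfall below 80% power. It costs about 39% more patients in the later trial (1.18² = 1.39).

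Sizing on the lower 95% confidence limit of the effect is not a workable substitute. At 12 v 9 that limit is zero or negative in about 81% of pilots at d = 0.5, so no sample size could be computed.

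The cost now is one sentence. Later, the efficacy trial may be planned larger than a favourable pilot would suggest. The investigators must also justify a minimum important difference for dual task interference, which these documents do not give. The gain shown above assumes that the true effect is at least as large as that target.
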